**Other Exclusions**

23. Breastfeeding at the time of the screening visit or planning to breastfeed at any time starting with the screening visit through end of the study treatment period
24. Known intolerance/hypersensitivity to volixibat or its components
25. Confirmed positive urine drug/alcohol screen at any time during pregnancy, including at the screening visit
26. Participating in another ongoing interventional clinical study at screening or planning to participate in another contemporaneous interventional clinical study while participating in this study; contemporaneous participation in studies that do not involve pharmaceuticals, devices, or other interventions and do not interfere with this study's (OHANA) schedule of activities (i.e., observational studies, registries) are permitted
27. History of nonadherence to medical regimens, unreliability, medical condition, mental instability, or cognitive impairment that, in the opinion of the investigator or medical monitor, may interfere with the interpretation of study results, could compromise the validity of informed consent, compromise the safety of the participant, or lead to nonadherence with the study protocol or inability to conduct the study procedures
28. Participant is in a dependent relationship with or has an immediate family member who is a study site employee that is involved in the conduct of this study (e.g., spouse, parent, child, or sibling) or participant is a study site employee.

### **Investigational Product, Dosage, and Mode of Administration**

Volixibat in capsules at doses of 20 mg and 80 mg and matched placebo will be supplied (in a blinded fashion for Part 2) for oral BID dosing. As much as possible, the morning dose (4 capsules) will be administered ~30 minutes before breakfast and the evening dose (4 capsules) will be administered 30 minutes before dinner to cover the luminal bile acid release associated with meals.

### **Statistical Methods**

All predefined statistical analyses for the final analysis will be performed after the database is locked. All statistical analyses will be performed using SAS software (SAS Institute, Cary, NC, USA) version 9.4 or higher.

### **Primary Analysis for Primary Efficacy Endpoints**

The primary analysis on the primary efficacy endpoint will be conducted in Part 2 using the modified intent-to-treat (mITT) population. A restricted maximum likelihood (REML)–based mixed-effects model for repeated measures (MMRM) will be used as the primary analysis method. The repeated measures include weekly postbaseline visits through Week 3, with the change from baseline in total sBA as the dependent variable. The MMRM model will include the fixed, continuous effects of baseline sBA and gestational age, fixed categorical effects of presence/absence of gestational diabetes, treatment group, visit, and treatment group-by-visit interaction and participant as a random effect.

The primary efficacy analysis will compare volixibat and placebo using the contrast (difference in least squares [LS] means) between treatment groups at Week 3. Significance tests will be based on LS means using a 2-sided significance level (2-sided 95% CIs).

The null hypothesis for the primary efficacy endpoint of the equality of volixibat and placebo is:

$$H_0: \text{mean change in total sBA baseline and Week 3 in the 2 treatment groups are equal}$$

Separately, a similar analysis on each of the open-label cohorts will be performed. The analysis will be identical, except that baseline sBA will not be a covariate used within the model.

### **Secondary Efficacy Endpoint Analyses**

The secondary efficacy endpoints are designed to evaluate the efficacy of volixibat versus placebo for the treatment of pruritus in participants with ICP as well as composite perinatal outcomes.

The secondary efficacy endpoint for pruritus is defined as the mean change from baseline to Week 3 in the weekly average worst daily itch score as measured by the Adult ItchRO. The worst daily itch score is averaged over the 7 days preceding baseline and over the 7 days preceding each week through Week 3. If >3 days of assessments are missing from a given week, then that weekly average will be set to missing. The analysis of the Adult ItchRO will use an MMRM with a comparable model to that for the primary endpoint. The primary comparison will be made regardless of adherence to randomized treatment, treatment modification, or treatment termination and irrespective of any changes in, or initiations of, allowed concomitant therapies, while assuming prohibited medications are not available and that delivery or perinatal death prior to 3 weeks does not occur.

The attributes for this estimand are the same as for the primary estimand except for the below:

- Endpoint: Change from baseline to Week 3 of the study treatment period in the weekly averaged worse daily itch score as measured by the Adult ItchRO (average of the 7 days preceding baseline and of the 7 days preceding Week 3).
- Population-level summary: Difference in the mean change in the weekly averaged worse daily itch score

The secondary efficacy endpoint for composite perinatal outcomes is defined as the proportion of participants that experience any of the 4 outcomes specified in the protocol. The comparison of interest is

the proportion of participants meeting the composite outcome. The primary comparison will be made regardless of adherence to randomized treatment, treatment modification, or treatment termination and irrespective of any changes in, or initiations of, allowed concomitant therapies, while assuming prohibited medications are not available.

The attributes for this estimand are the same as for the primary estimand except for the below:

- Treatments: The randomized treatment administered BID until day of delivery (with at least 1 dose), regardless of adherence to randomized treatment, treatment modification, or treatment termination.
- Endpoint: Experiencing one or more of perinatal death, spontaneous preterm delivery, iatrogenic preterm delivery attributed to ICP or ICP-related complications, neonatal unit admission for  $\geq 12$  hours from birth until hospital discharge for one or more of predefined indications.
- Population-level summary: Difference between treatment groups in the proportion of participants achieving the endpoint.
- Intercurrent events: Preterm delivery or perinatal death are included as part of the endpoint definition and thus handled using a composite strategy.

For this responder-type endpoint, the number and proportion of participants that are considered a “responder” will be summarized by treatment group at Week 3 and analyzed using a stratified Cochran-Mantel-Haenszel (CMH) test to calculate the p-value for the difference between treatment groups. The p-value from the CMH test will be the basis of the hypothesis testing. Furthermore, as supportive analyses, a Logistic Regression (LR) estimator approach, as well as a logistic regression model with baseline sBA, gestational age, and presence/absence of gestational diabetes as covariates will be run.

All tests will be performed as 2-sided tests at the 0.05 level of significance.

### **Safety Analyses**

All safety analyses will be performed on the safety population, defined as all participants who were randomized and received at least 1 dose of study medication.

For all safety and tolerability analyses, participants will be analyzed by the treatment received and the overall active treatment group. For active treatment, the dose received will be used.

Safety data collected at the baseline visit or the last preceding visit (if not collected at the baseline visit) will be used as the baseline value for safety analyses.

Safety measures include AEs, clinical laboratory values, physical examination findings (including body weight, height, and body mass index), vital signs, and concomitant treatment usage. For quantitative variables, descriptive statistics including number of observations, mean, median, standard deviation, minimum, and maximum will be presented for observed and change from baseline values at each study visit. Qualitative variables will be summarized using counts and percentages.

### **Interim Analysis**

A formal interim analysis will be conducted at the end of Part 1, which will inform sample size for Part 2 as well as dose selection. There will be ongoing data review during Part 1 after every ~20 participants are enrolled in this open-label setting. Data from Part 1 will be included in the overall safety and tolerability summaries but will not be combined with those from Part 2 for the statistical inference performed in Part 2.

[figure not shown]
**Sample Size Determination**

Part 1 of the study is designed for estimation without formal statistical testing; hence, there are no formal power considerations. For example, with 20 participants per group and assuming a standard deviation of 25 for each group, a 95% CI for the mean for each volixibat arm would have a half width of 11.

For the power calculations for Part 2, it is assumed that only a single dose will be selected at the end of Part 1, and a 2-sided alpha 0.05 will be used to test whether there is a difference between the 2 groups. Thus, for Part 2, a sample size of 100 participants per arm has 80% power to detect mean difference of 10 with standard deviation of 25. Power was calculated using SAS, version 9.4.

[figure not shown]
## 1.2. Study Schema

Figure 1 Part 1: Open Label (Proof of Concept)

BID=twice daily; PK=pharmacokinetic; R=randomization; sBA=serum bile acid; VLX=volixibat.

Figure 2 Part 2: Double Blind (Confirmatory Analysis)

PK=pharmacokinetic; QoL=quality of life; R=randomization; sBA=serum bile acid; VLX=volixibat.

### 1.3. Schedule of Activities

**Table 1 Schedule of Activities**

Visit Name	Screening	Treatment Period				Follow-Up		Notes
		Baseline	Weeks 1, 2, 3, etc.	Early Termination*	EOT/Delivery	F1	F2 (EOS)	
Day/Week (Window)	Day -10 to -1	0*	Every 7 Days (±1 Day) Until Delivery		Day of Delivery (+2 Days)	Phone Call: 14 Days after Delivery (±3 Days)	Clinic Visit: 28 Days after Delivery (±3 Days)	
*Participants who early terminate from study drug should still continue with weekly visits through delivery, F1, and F2.
 
Some visits may be conducted as a home health or remote visit at the discretion of the investigator upon approval by the sponsor or designee and in accordance with local and regional regulations.
 
*See Section 8.1.8 for further details on timing of baseline visit.

Administrative Procedures								
Informed consent	X							
Eligibility Procedures								
Inclusion/exclusion criteria	X	X						
Demography	X							
Prior/concomitant treatment	X	X	X	X	X	X	X	
Medical history	X	X						Includes menstrual and obstetric history
Estimated gestational age assessment	X							Confirmation of eligibility based upon estimated gestational age required before randomization: CRL from early ultrasound or head circumference on ultrasound if CRL is >84 mm.

Visit Name	Screening	Treatment Period				Follow-Up		Notes
		Baseline	Weeks 1, 2, 3, etc.	Early Termination*	EOT/Delivery	F1	F2 (EOS)	
Day/Week (Window)	Day -10 to -1	0*	Every 7 Days (±1 Day) Until Delivery		Day of Delivery (+2 Days)	Phone Call: 14 Days after Delivery (±3 Days)	Clinic Visit: 28 Days after Delivery (±3 Days)	*Participants who early terminate from study drug should still continue with weekly visits through delivery, F1, and F2.  Some visits may be conducted as a home health or remote visit at the discretion of the investigator upon approval by the sponsor or designee and in accordance with local and regional regulations. *See Section 8.1.8 for further details on timing of baseline visit.
Hepatitis and HIV screen, TSH	X							If HIV results are documented as negative from the current pregnancy in a participant deemed to be low risk by the investigator, HIV at screening visit may be waived.
Dosing Procedures								
Randomization		X						
Study drug dispensing		X	X					As needed
Study drug collection/reconciliation			X	X	X			As needed
Efficacy Procedures								
Education and compliance assessment of pruritus assessments	X	X	X					Education regarding importance of eDiary compliance at screening visit; reinforcement regarding eDiary compliance at study visits (as needed).
Once daily Adult ItchRO score assessment	X	X	X	X	X			Participant completes ItchRO at home on eDiary up to and including the day of delivery.

Visit Name	Screening	Treatment Period				Follow-Up		Notes
		Baseline	Weeks 1, 2, 3, etc.	Early Termination*	EOT/Delivery	F1	F2 (EOS)	
Day/Week (Window)	Day -10 to -1	0*	Every 7 Days (±1 Day) Until Delivery		Day of Delivery (+2 Days)	Phone Call: 14 Days after Delivery (±3 Days)	Clinic Visit: 28 Days after Delivery (±3 Days)	
*Participants who early terminate from study drug should still continue with weekly visits through delivery, F1, and F2.
 
Some visits may be conducted as a home health or remote visit at the discretion of the investigator upon approval by the sponsor or designee and in accordance with local and regional regulations.
 
*See Section 8.1.8 for further details on timing of baseline visit.

Pruritus/QoL PRO assessments (5D itch scale, EQ-5D-5L, PROMIS SF v1.0-Fatigue 7a, PROMIS SF v1.0 - Sleep Disturbance, PIS-Itch)	X*	X**	X***	X	X****			
Participant completes at clinic.
 
All PRO assessments to be completed by participant, including PIS-Itch and PGIC-Itch, should be collected prior to additional procedures at study visits.
 
*Participant to complete paper PIS-Itch at screening. This score will be captured in the EDC by site staff.
 
** Participant may complete all the PRO assessments at home before they arrive onsite for the baseline visit (Day 0).
 
*** At Week 3 visit only
 
**** For participants who terminate from study drug early, this does not need to be repeated.

PGIC-Itch			X*	X	X**			
Participant completes at clinic.
 
*At Week 3 visit only
 
**For participants who terminate from study drug early, this does not need to be repeated.

Visit Name	Screening	Treatment Period				Follow-Up		Notes
		Baseline	Weeks 1, 2, 3, etc.	Early Termination*	EOT/Delivery	F1	F2 (EOS)	
Day/Week (Window)	Day -10 to -1	0*	Every 7 Days (±1 Day) Until Delivery		Day of Delivery (+2 Days)	Phone Call: 14 Days after Delivery (±3 Days)	Clinic Visit: 28 Days after Delivery (±3 Days)	
*Participants who early terminate from study drug should still continue with weekly visits through delivery, F1, and F2.
 
Some visits may be conducted as a home health or remote visit at the discretion of the investigator upon approval by the sponsor or designee and in accordance with local and regional regulations.
 
*See Section 8.1.8 for further details on timing of baseline visit.

CSS		X	X*	X	X		X	
To the extent possible, CSS assessments should be made by the same investigator or designee during study visits.
 
*At Week 3 visit only.

Other Procedures								
Health utilization		X		X			X	
Safety Procedures								
Drug and alcohol screen	X							
Physical examination	X	X	X	X	X		X	Complete examination conducted at screening and F2 visits. A symptom-directed examination focused on changes from last examination conducted at other visits. Includes confirmation of fetal cardiac activity via Doppler/auscultation at each visit while participant is pregnant.
Height	X							
Weight	X	X	X	X	X		X	

Visit Name	Screening	Treatment Period				Follow-Up		Notes
		Baseline	Weeks 1, 2, 3, etc.	Early Termination*	EOT/Delivery	F1	F2 (EOS)	
Day/Week (Window)	Day -10 to -1	0*	Every 7 Days (±1 Day) Until Delivery		Day of Delivery (+2 Days)	Phone Call: 14 Days after Delivery (±3 Days)	Clinic Visit: 28 Days after Delivery (±3 Days)	
*Participants who early terminate from study drug should still continue with weekly visits through delivery, F1, and F2.
 
Some visits may be conducted as a home health or remote visit at the discretion of the investigator upon approval by the sponsor or designee and in accordance with local and regional regulations.
 
*See Section 8.1.8 for further details on timing of baseline visit.

ECG	X							ECG is not a required study procedure; however, a local ECG at or after screening visit may be performed at the investigator's discretion.
Vital signs	X	X	X	X	X		X	
Hematology	X		X	X	X		X	
Chemistry	X		X	X	X		X	
Coagulation panel (PT/INR, PTT)	X		X	X	X		X	
Vitamin A, D, and E levels		X	X*		X		X	*Every 4 weeks, starting with Week 4 visit. The sample collection tube should be protected from light.
Urinalysis	X	X	X	X	X		X	
Lipid panel, glycated albumin	X		X*		X		X	*Every 2 weeks, starting with Week 2 visit
AE review		X	X	X	X	X	X	AEs for mother and baby to be collected and reviewed for up to 30 days after respective dates of hospital discharge. See Section 8.3.1 for further details.

Visit Name	Screening	Treatment Period				Follow-Up		Notes
		Baseline	Weeks 1, 2, 3, etc.	Early Termination*	EOT/Delivery	F1	F2 (EOS)	
Day/Week (Window)	Day -10 to -1	0*	Every 7 Days (±1 Day) Until Delivery		Day of Delivery (+2 Days)	Phone Call: 14 Days after Delivery (±3 Days)	Clinic Visit: 28 Days after Delivery (±3 Days)	
*Participants who early terminate from study drug should still continue with weekly visits through delivery, F1, and F2.
 
Some visits may be conducted as a home health or remote visit at the discretion of the investigator upon approval by the sponsor or designee and in accordance with local and regional regulations.
 
*See Section 8.1.8 for further details on timing of baseline visit.

Fetal ultrasound	X*	X*	X**					
* First ultrasound may be done during screening OR baseline (both are not required). The first study ultrasound (screening or baseline) may be waived if an ultrasound was already performed within 1 week prior to screening and should be captured in the eCRF on the screening ultrasound page.
 
** Every 4 weeks while on study drug

Antepartum fetal monitoring (NST/CTG or BPP)		X						At baseline visit only, and thereafter at the discretion of the investigator

Visit Name	Screening	Treatment Period				Follow-Up		Notes
		Baseline	Weeks 1, 2, 3, etc.	Early Termination*	EOT/Delivery	F1	F2 (EOS)	
Day/Week (Window)	Day -10 to -1	0*	Every 7 Days (±1 Day) Until Delivery		Day of Delivery (+2 Days)	Phone Call: 14 Days after Delivery (±3 Days)	Clinic Visit: 28 Days after Delivery (±3 Days)	
*Participants who early terminate from study drug should still continue with weekly visits through delivery, F1, and F2.
 
Some visits may be conducted as a home health or remote visit at the discretion of the investigator upon approval by the sponsor or designee and in accordance with local and regional regulations.
 
*See Section 8.1.8 for further details on timing of baseline visit.

Perinatal outcomes assessment					X			
Outcomes include
 
 
• Gestational age at delivery
 
• Mode of delivery (e.g., vaginal, operative vaginal, Cesarean, etc.; and iatrogenic vs. spontaneous)
 
• Indication(s) for delivery, if iatrogenic
 
• Maternal estimated blood loss at delivery
 
• Apgar score at 5 minutes
 
• Infant/placenta weight
 
• Presence/absence of meconium staining of amniotic fluid
 
• Neonatal diagnoses and data, including NICU data if applicable
 

Umbilical cord sample (at delivery, when possible)					X			
Umbilical artery pH should be assessed first, followed by volixibat pharmacokinetics. Thereafter, sBA, total cholesterol, LDL cholesterol, and glucose can be assessed in any order.

Genetics – maternal blood (optional)		X						
Specific testing TBD. Must confirm specific consent has been obtained for genetic testing

Visit Name	Screening	Treatment Period				Follow-Up		Notes
		Baseline	Weeks 1, 2, 3, etc.	Early Termination*	EOT/Delivery	F1	F2 (EOS)	
Day/Week (Window)	Day -10 to -1	0*	Every 7 Days (±1 Day) Until Delivery		Day of Delivery (+2 Days)	Phone Call: 14 Days after Delivery (±3 Days)	Clinic Visit: 28 Days after Delivery (±3 Days)	
*Participants who early terminate from study drug should still continue with weekly visits through delivery, F1, and F2.
 
Some visits may be conducted as a home health or remote visit at the discretion of the investigator upon approval by the sponsor or designee and in accordance with local and regional regulations.
 
*See Section 8.1.8 for further details on timing of baseline visit.

Genetics – cord blood sample (optional)					X			Specific testing TBD. Must confirm specific consent has been obtained for genetic testing.
NICU admission					X	X	X	Collect NICU admissions diagnoses and data for the duration of NICU stay (i.e., follow to resolution).
Drug Levels/Biomarkers Procedures								
Volixibat concentration sample (maternal plasma)			X*	X	X			
*At Weeks 1 and 3 visit, 3 hours (±1 hour) post-dose
 
When feasible, maternal sample should be collected as close to time of actual delivery as possible.
 
Drug level sampling may be discontinued in Part 2 pending Part 1 results

Volixibat concentration sample (fetal plasma from umbilical cord at delivery, when possible)					X			Drug level sampling may be discontinued in Part 2 pending Part 1 results

Visit Name	Screening	Treatment Period				Follow-Up		Notes
		Baseline	Weeks 1, 2, 3, etc.	Early Termination*	EOT/Delivery	F1	F2 (EOS)	
Day/Week (Window)	Day -10 to -1	0*	Every 7 Days (±1 Day) Until Delivery		Day of Delivery (+2 Days)	Phone Call: 14 Days after Delivery (±3 Days)	Clinic Visit: 28 Days after Delivery (±3 Days)	
*Participants who early terminate from study drug should still continue with weekly visits through delivery, F1, and F2.
 
Some visits may be conducted as a home health or remote visit at the discretion of the investigator upon approval by the sponsor or designee and in accordance with local and regional regulations.
 
*See Section 8.1.8 for further details on timing of baseline visit.

sBA	X	X*	X*	X	X**		X	
At each visit except EOT/Delivery, sBA should be drawn 30-90 minutes postprandially, whenever possible). Every effort should be made to collect sBA levels at approximately the same time of day (morning, midday, or afternoon) at each visit starting with baseline, except for EOT/delivery.
 
*At baseline and Week 3, there will be 2 samples collected.
 
**At EOT/Delivery, there will be 2 samples collected, without regard to last meal.

Postprandial biomarker samples (maternal) 
 
• 7<math>\alpha</math>C4 (postprandial, 30-90 minutes)
 
• FGF-19
 
• Autotaxin
 
• Progesterone sulfate
 
• GLP-1
 
		X	X*		X			
Prior to the sample collection, all participants are strongly encouraged to eat a meal within approximately 30-90 minutes (whenever possible). Every effort should be made to collect biomarker sample collection at approximately the same time of day (morning, midday, or afternoon) at each visit.
 
*At Week 3 visit only

5-D Itch; Adult Itch RO; 7 $\alpha$ C4=7 $\alpha$ -hydroxy-cholesten-3-one; AE=adverse event; BPP=biophysical profile; CRL=crown rump length; CSS=Clinician Scratch Scale; CTG=cardiotocography; eCRF=electronic case report form; eDiary=electronic diary; EDC=electronic data capture; EOS=end of study; EOT=end of treatment;

EQ-5D-5L=EuroQoL 5-Dimension 5-Level; ET=early termination; F1=Follow-Up Visit 1; F2=Follow-Up Visit 2; INR=international normalized ratio; ItchRO=Itch Reported Outcome; LDL=low-density lipoprotein; NICU=neonatal intensive care unit; NST=nonstress test; PGIC-Itch=Patient Global Impression of Change-Itch; PIS-Itch=Patient Impression of Severity-Itch; PRO=patient-reported outcome; PROMIS=Patient-Reported Outcomes Measurement Information System; PT=prothrombin time; PTT=partial thromboplastin time; QoL=quality of life; sBA=serum bile acid; SF=short form; TBD=to be determined; TSH=thyroid-stimulating hormone.

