## 7. DISCONTINUATION OF STUDY DRUG AND PARTICIPANT WITHDRAWAL CRITERIA

### 7.1. Discontinuation of Study Drug

Participants may elect to discontinue study drug at any time for any reason.

Whenever possible, participants who discontinue study drug should continue in the study on a weekly visit schedule until completion of F2, 28 ( $\pm 3$ ) days after delivery as outlined in the SoA ([Table 1](#)).

A participant will be discontinued from study drug for any of the following reasons:

- Withdrawal of consent by the participant
- Emergency unblinding of treatment assignment by the investigative site
- Criteria for stopping drug due to suspected DILI are met (refer to [Appendix 3](#))
- Any AE or progression of ICP refractory to rescue medication use that leads the investigator to decide that the participant should be withdrawn from study drug, including but not limited to the following:  
Any AE of Common Terminology Criteria for Adverse Events (CTCAE) Grade 4, related to study drug
- Evidence of hepatic decompensation, including variceal bleeding, hepatic encephalopathy and/or ascites

- In the opinion of the investigator or study medical monitor, it is medically unacceptable or otherwise not in the participant's best interest to continue with study drug
- Gross noncompliance, including failure to adhere to the study requirements as stated in the study protocol.

Refer to the SoA (Table 1) for data to be collected at the time of end of treatment and follow-up and for any further evaluations that need to be completed.

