#### **8.1.13. Delivery Visit**

Delivery may occur at a hospital other than clinical site in the event of an emergency. For the Delivery Visit, the investigator/clinical coordinator can visit the delivery hospital or the participant can visit the investigative site after delivery. Whenever possible, every effort should be made to collect all assessments specified in the SoA ([Table 1](#)) for this visit, especially the PRO/quality-of-life assessments, within 24 hours after delivery.

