### **10.4.3. Other Analyses**

#### **10.4.3.1. Patient-Reported Outcomes**

The effect of volixibat on additional measures of pruritus efficacy and quality of life in adult participants with ICP will be evaluated via the following endpoints:

- Change from baseline in the 5-D Itch Scale
- Change from baseline in CSS
- Change from baseline in EQ-5D-5L
- Change from baseline in PROMIS SF Fatigue 7a
- Change from baseline in PROMIS SF Sleep Disturbance
- Change from baseline in PIS-Itch

Because the PROs are administered only at baseline, Week 3, and end of treatment, the change from baseline will be compared between the 2 groups with use of rank ANCOVA with adjustment for baseline with the Mann-Whitney odds as the estimand. The estimates and CIs can be calculated using the R package sanon ([Kawaguchi and Koch 2015](#)).

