### 3.8.2. Analysis Visit Windows

Participant visits might not occur on protocol-specified days. Therefore, for the purpose of analysis, observations will be assigned to analysis windows. A notable exception to the analysis visit windows below is the end of treatment/date of delivery. This will be summarized as its own visit and that will be the value used for endpoints that look at either the value or change from baseline to delivery.

The analysis windows for ItchRO, sBA, hematology, chemistry, coagulation, weight, vital Signs, and urinalysis are provided in [Table 2](#).

The analysis windows for 5-D Itch, EQ-5D-5L, PROMIS Fatigue and Sleep patient reported outcomes (PROs), PIS-Itch, PGIC-Itch, and Biomarker samples (7 $\alpha$ -hydroxy-cholesten-3-one [7 $\alpha$ C4], fibroblast growth factor 19 [FGF-19], autotaxin, progesterone sulfate, and glucagon-like peptide 1 [GLP-1]) are provided in [Table 3](#).

The analysis windows for lipid panel and glycated albumin are provided in [Table 4](#).

The analysis windows for vitamin A, D, and E levels and fetal ultrasound are provided in [Table 5](#).

**Table 2 Analysis Visit Windows for ItchRO^, sBA, Hematology\*, Chemistry\*, Coagulation\*, Weight, Vital Signs, and Urinalysis**

Nominal Visit	Nominal Study Day	Lower Limit	Upper Limit
Baseline	1	(none)	1
Week 1	8	2	11
Week K (K is every week after previous visit)	K*7 + 1	K*7 – 2	K*7 + 4

^ ItchRO is collected daily, but will have weekly averages calculated and results will be grouped according to the analysis windows above.

\* Hematology, chemistry, and coagulation are not planned to be collected at the baseline visit. Rather, the screening visit (or a subsequent unscheduled visit) will serve as the baseline.

**Table 3 Analysis Visit Windows for 5-D Itch, CSS, EQ-5D-5L, PROMIS Fatigue and Sleep PROs, PIS-Itch, PGIC-Itch, and Biomarker Samples (C4, FGF-19, Autotaxin, Progesterone Sulfate, GLP-1)**

Nominal Visit	Nominal Study Day	Lower Limit	Upper Limit
Baseline*	1	(none)	1
Week 3	22	19	25

\*PGIC-Itch was not collected at baseline.

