## 8. PATIENT-REPORTED OUTCOMES

To evaluate QoL in participants with ICP-associated pruritus treated with volixibat versus placebo on the basis of the following endpoints:

- Change in 5-D Itch scale with 1-week recall from baseline to Week 3 and delivery
- Change in Clinician Scratch Scale (CSS) from baseline to Week 3 and delivery
- Change in EQ-5D-5L from baseline to Week 3 and delivery
- Change in PROMIS fatigue score from baseline to Week 3 and delivery
- Change in PROMIS sleep score from baseline to Week 3 and delivery
- Change in Patient Impression of Severity of Itch (PIS-Itch) from baseline to Week 3 and delivery
- PGIC-Itch at Week 3 and delivery

Because the PROs are administered only at baseline, Week 3, and end of treatment, the change from baseline will be compared between the two groups with use of rank ANCOVA with adjustment for baseline with the Mann-Whitney odds as the estimand. The estimates and CIs can be calculated using the R package sanon ([Kawaguchi and Koch 2015](#)).

Additionally, the difference between treatment groups in the change from baseline at Week 3 and, separately, at delivery, will be evaluated using an ANCOVA model with fixed, categorical effects of treatment group, visit, and treatment group-by-visit interaction as well as the continuous, fixed covariates of baseline and the baseline-by-visit interaction. LS means will be calculated for each treatment group in the model. The difference between volixibat and placebo change from baseline in each outcome variable will be estimated, with the corresponding 2-sided 95% CI constructed for each visit. Change from baseline LS means with standard error, 95% CI for the LS means, p-value for testing if the LS mean is zero, LS mean difference between treatment groups (volixibat minus placebo) with standard error, 95% CI for the LS mean difference, and p-value for testing if the treatment LS means are equal will be calculated for each visit. The number of observations, mean, 95% CI on the mean, standard deviation, median, minimum, and maximum on both the observed and change from baseline values will also be summarized by treatment group for each visit.

For PGIC-Itch, since the PRO is a measure of change without a defined baseline, an ANCOVA model will be used, but will not include fixed covariates of baseline and the baseline-by-visit interaction. The dependent variable will be the PGIC-Itch value.

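### Delivery questionnaires are optional for participants who stop study drug early, and the SAP has no rule for their early-termination scores, so the exploratory delivery PRO comparison may under-represent or exclude them

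*Protocol*

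**What the plan says.** **Schedule.** Protocol Table 1 marks the PRO battery (5-D Itch, EQ-5D-5L, PROMIS Fatigue, PROMIS Sleep Disturbance, PIS-Itch) and, in its own row, PGIC-Itch at Week 3, Early Termination and EOT/Delivery. The EOT/Delivery cell of each row carries the note "For participants who terminate from study drug early, this does not need to be repeated". SAP Appendix 1, Table 7, repeats both notes.

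**Follow-up after stopping drug.** Table 1 states: "Participants who early terminate from study drug should still continue with weekly visits through delivery, F1, and F2". Protocol 7.1 agrees: whenever possible, "participants who discontinue study drug should continue in the study on a weekly visit schedule until completion of F2".

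**Delivery visit.** Protocol 8.1.13 says: "Whenever possible, every effort should be made to collect all assessments specified in the SoA" "for this visit, especially the PRO/quality-of-life assessments, within 24 hours after delivery". It makes no exception for participants off drug.

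**Analysis.** SAP Section 8 lists delivery as a time point for every PRO, for example "Change in 5-D Itch scale with 1-week recall from baseline to Week 3 and delivery", and plans between-arm differences with confidence intervals and p-values. SAP Table 3 gives these instruments two windows, baseline and Week 3 (Days 19 to 25). Of the end-of-treatment/delivery record, SAP 3.8.2 says: "This will be summarized as its own visit". No rule assigns an Early Termination record. SAP 3.6.1 imputes nothing unless a method is specified, and none is specified for PROs.

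**The concern.** The waiver is triggered by stopping study drug, which happens after randomization and can depend on treatment. The protocol itself anticipates stopping because of gastrointestinal intolerance (6.2, 6.8.1.1) and because of ICP progression refractory to rescue medication (7.1). If sites use the waiver, delivery PROs are missing for a group selected in this way, although those women are still under follow-up. The schedule, not loss of contact, creates the gap, and data not collected at delivery cannot be recovered later.

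At stake is the delivery contrast for six questionnaires. PIS-Itch and PGIC-Itch are also anchors for meaningful change in Adult ItchRO (Protocol Appendices 8 and 9), so missing delivery values thin that evidence too.

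**Working it through.** **1. Which early-termination records can be used.** The SAP Table 2 formula with K = 3 gives nominal day 3×7+1 = 22, lower limit 3×7−2 = 19 and upper limit 3×7+4 = 25. This matches the Week 3 row of Table 3. An Early Termination PRO record therefore:
- on Days 19 to 25 is eligible for Week 3;
- on Days 2 to 18, or after Day 25, falls in no window.

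SAP 3.8.3 does remap a delivery value obtained before Week 3. It has no matching rule for Early Termination.

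**2. Whether such a record could serve as the second time point.** Protocol 4.1 and SAP 1.2 define the end of the treatment period as the day of delivery, and SAP 3.8.2 treats end of treatment and date of delivery as one visit. On those definitions an Early Termination record is not the delivery value. Yet Protocol 10.4.3.1 says "Because the PROs are administered only at baseline, Week 3, and end of treatment", SAP Section 8 repeats that sentence, and the SAP endpoint list says delivery. Nothing states the choice for someone who stopped early.

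**3. Loss of data at 100 per arm.** The stopping rates are assumptions; the documents give none. Let d be the share stopping drug and f the share of those who still complete the delivery PROs. The number with data is 100×(1−d(1−f)).

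| d | f = 0: n (SE factor) | f = 0.5: n | f = 0.5: share of n who stopped drug |
|---|---|---|---|
| 5% | 95 (1.03) | 97.5 | 2.6% |
| 10% | 90 (1.05) | 95 | 5.3% |
| 20% | 80 (1.12) | 90 | 11.1% |

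Precision changes little. Selection is the larger issue.

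**4. Bias with full use of the waiver (f = 0).** Let g be the stopper-minus-completer mean in SD units, with higher scores worse. An arm's full mean is its completer mean plus d×g. Restricting to completers therefore shifts the volixibat-minus-placebo difference by −(d_V×g_V − d_P×g_P). With a common g its size is |d_V − d_P|×g.

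| Assumed stopping, volixibat / placebo | g | Bias (SD) | SE (SD) | Bias / SE |
|---|---|---|---|---|
| 15% / 5% | 0.5–1.0 | 0.05–0.10 | √(1/85+1/95) = 0.149 | 0.33–0.67 |
| 10% / 5% | 0.5–1.0 | 0.025–0.05 | √(1/90+1/95) = 0.147 | 0.17–0.34 |
| equal rates | equal | 0 | – | 0 |

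With the rates reversed between arms, the bias has the same size and the opposite sign.

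**5. Bias with partial use (f = 0.5, 15% / 5%).** Stoppers make up 0.075/0.925 = 8.1% and 0.025/0.975 = 2.6% of observed data. The shortfalls are 15.0−8.1 = 6.9 and 5.0−2.6 = 2.4 points. The difference of about 4.5 points gives 0.022 to 0.045 SD for g of 0.5 to 1.0.

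**The case against.** The best defence is that little depends on this. The endpoints are exploratory and outside the testing hierarchy. Week 3 PROs are not waived, so early stoppers still in follow-up remain in that comparison. Adult ItchRO, the itch endpoint in the hierarchy, is collected through the day of delivery. In the current protocol CSS has its own row with no waiver. Stopping may also be uncommon: Protocol 4.4 reports no discontinuation for diarrhea or cramping in VLX-103, and 6.2 calls for a dose interruption or reduction to be offered before a tolerability discontinuation. All of this stands and limits the importance of the point, although VLX-103 enrolled healthy volunteers.

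Four stronger readings are tempting, and the documents do not support them.

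- **Table 1 forbids the delivery questionnaires.** The note is permissive, and 8.1.13 pulls the other way.
- **The delivery comparison covers only drug completers.** That needs every site to use the waiver every time and no Early Termination record to be analysed as end of treatment. Neither is established.
- **Every early-termination score is lost.** Those on Days 19 to 25 are eligible for Week 3.
- **The protocol says end of treatment where the SAP says delivery.** Both contain the same sentence. The loose wording is within the SAP's own Section 8.

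**Conclusion.** The point holds as a limited one. Both schedules make delivery PROs optional after early drug discontinuation. This is at odds with Protocol 8.1.13, and the SAP neither assigns Early Termination records outside Days 19 to 25 nor plans imputation for PROs. The SAP's supplementary ANCOVA includes visit terms but states no within-participant correlation, so it cannot be relied on to fill the delivery gap from Week 3 scores. The exploratory delivery comparison may therefore under-represent or exclude women who stopped drug.

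Neither the size nor the direction of the bias can be determined from the documents. The 0.05 to 0.10 SD figure rests on assumed stopping rates of 15% versus 5%, an assumed common gap of 0.5 to 1.0 SD and full use of the waiver. It stays below one standard error in each case shown. More stopping on placebo, for example for persistent itch, would shrink or reverse it. No confirmatory claim is touched. The change is worth making because it is cheap and the data cannot be obtained afterwards.

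**What to change.** - **Protocol Table 1:** delete the early-stopper note from the PRO and PGIC-Itch rows, so that all participants still in follow-up complete the questionnaires at EOT/Delivery, in line with 8.1.13.
- **SAP Appendix 1, Table 7:** delete the same two notes. CSS still sits inside the waived PRO row there, because the SAP follows protocol Version 1; give it its own row as in the current protocol.
- **SAP 3.8 and Section 8:** use delivery as the single name for the second time point. State that the delivery value is analysed regardless of study-drug status, that Early Termination records are summarised separately, and whether a record on Days 19 to 25 may also serve as Week 3. Say how missing delivery PROs are handled.
- **Reporting:** show by arm how many stopped drug early and how many of those have delivery PROs.

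The cost is text edits in two documents and one more questionnaire set for early stoppers, at a visit already scheduled.
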